Primary study endpoints– Phase I & IIa: 
• Evaluate the adverse events (Toxicity Grading Scale for Healthy Adult and Adolescent Volunteers Enrolled in Preventative Vaccine Clinical Trials)• Determine of GMT and seroconversion rate of SARS-CoV-2 Spike and ORF3a protein specific binding antibody responses induced by GLS-5310 relative to treatment arm (Endpoint titer of binding antibody in serum at each timepoint)
Secondary study endpoints– Phase I & IIa: 
• Determine the positive responder rate of T cell responses induced by GLS-5310 (Antigen-specific interferon gamma (IFN-γ) secretion T-cell response in PBMC at each timepoint)• Determine of GMT and positive responder rate of the neutralizing antibody response induced by GLS-5310 (plaque-reduction neutralizing titer in serum at each timepoint)

Exploratory study endpoints**Phase I**

- Determine binding antibody responses after a single dose of vaccine related to treatment arm (Endpoint titer of binding antibody in serum at each timepoint)
- Determine whether passive transfer of human serum can protect against pulmonary infection from SARS-CoV-2 challenge in an animal infection model (Survival rate, blood and viral load measurement of major organs, pathological examination of respiratory/lung area, immunogenicity evaluation)

Phase IIa

- Determine the persistence of immune responses following vaccination with GLS-5310 (Endpoint titer of binding antibody in serum at each timepoint, Antigen-specific interferon gamma (IFN- γ) secretion T-cell response in PBMC at each timepoint, plaque-reduction neutralizing titer in serum at each timepoint)
- Determine the extent of immune boosting for participants who are seropositive at baseline following vaccination with GLS-5310 (Endpoint titer of binding antibody in serum at each timepoint, Antigen-specific interferon gamma (IFN- γ) secretion T-cell response in PBMC at each timepoint, plaque-reduction neutralizing titer in serum at each timepoint)
- Determine whether immune responses to GLS-5310 of participants age 66-85 years differ from those age 65 years and younger.

Table S1: Dosing arms and treatment regimen

Study Phase	Study Arm	N	Route	GLS-5310 Dose	Vaccination schedule	Table of events
1	1a	15	ID	0.6 mg	0 – 8 weeks	S2
1	1b	15	ID	1.2 mg	0 – 8 weeks	S2
1	1c	15	ID	1.2 mg	0 – 12 weeks	S3
2	2a	40	ID	Placebo	0 – 8 weeks	S2
2	2b	80	ID	1.2 mg	0 – 8 weeks	S2

Study design:

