9.2 Immunogenicity assessments

9.2.1 SARS-CoV-2 Binding ELISA

Standardized ELISA assays will be performed to measure the anti-SARS-CoV-2 S and ORF3a binding antibody responses. Samples will be scored as positive if the average optical density (OD) is greater than 0.10 absorbance units and greater than the average OD before immunization plus 2.5 times the standard deviation (SD) of the OD before immunization at the same dilution. Results will be presented as the geometric mean titer (GMT) of the antibody titer, end-point titer, i.e. the last dilution where the OD value is above the calculated threshold.

The definition of seroconversion as a positive response post-baseline at the lowest dilution tested (i.e. and antibody titer that is below 1:100 at baseline and after vaccination positive at or above the 1:100 dilution) assuming that the baseline response would be negative at 1:100. The criteria for the appropriate immunogenicity of the SARS-CoV-2 binding antibody is planned to have a positive response rate of 70% or more in each group at the interim analysis.

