11.1 Data Sets to be Analyzed

- The intention to treat population (ITT) includes all participants who sign informed consent.
- The modified intention to treat population (mITT) includes all participants who sign informed consent and who has received at least one administration of study drug. The mITT population will be the primary analysis population for outcomes.
- The safety set (SS) includes all participants who have received at least one dose of study medication. The SS will be the primary group for safety evaluations and outcome. Analysis of immune responses will be performed only for available samples.

Per-protocol (PP) analysis set includes all participants who complete the trial and who receive all vaccinations and have no significant protocol violations. Participants in this sample will be grouped to treatment arms they actually received. This set will be used as a sensitivity analysis to summarize the primary and secondary efficacy outcomes. For secondary and exploratory assessments of antibody and T cell immune responses, denominators will include only those participants who are SARS-CoV-2 seronegative at baseline. Unevaluable samples will not be considered as part of the denominator at relevant time points. For study participants who are seropositive at baseline, separate assessment of antibody and T cell responses will be performed.

The Phase IIa portion of the study will be unblinded at the post-vaccination visit (visit 4) and all persons who were randomized to the placebo arm offered vaccination with GLS-5310. Safety assessments will be determined based on the actual treatment received. Persons randomized to the placebo group who elect vaccination with GLS-5310 will then be considered to cross-over to the vaccination group as of Week 12. Persons randomized to the placebo group, and who decline vaccination will remain as part of the placebo group, regardless of whether such persons receive any other COVID-19 vaccine. Any study participant who receives an approved COVID-19 vaccine will remain as part of the group assignment as above.

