4.1 Interim Analysis

Interim analyses were performed in stages.

- **Stage 1:** An assessment of AE's was performed after study Visit 1 for Group 1a.
- **Stage 2:** When all Phase I subjects (Groups 1a, 1b and 1c) had completed Visit 4, an interim analysis was performed to evaluate safety and antibody response.
In order for the study to move into Phase IIa study, the seroconversion rate for the binding antibody responses must be >70%. In addition, the incidence of Serious Adverse Events (Grade 3 or higher) related to the investigational product should be no more than 1 case.
- **Stage 3:** An interim analysis of Phase IIa study was performed after all patients complete their Visit 4. The purpose of this interim analysis was to provide options to placebo vaccinated subjects and to assess the safety of the vaccine after the second dose. For the interim analysis of Phase IIa, database locking was implemented before unblinding.

The study is unblinded at the post-vaccination visit (study Visit 4) at which time subjects are informed of their treatment assignment. Subjects who were assigned to the placebo group are offered to be vaccinated with GLS-5310. Subjects assigned to the placebo group who choose to be vaccinated with GLS-5310 are followed for a year from 1st GLS-5310 vaccination; subjects assigned to the placebo group but who decline vaccination with GLS-

CONFIDENTIAL

5310 are followed for a year from study entry as per the original study protocol.

5. Determination of Sample Size

This is an exploratory and descriptive Phase I/Ila clinical trial to evaluate the safety and immunogenicity of GLS-5310 for the purpose of preventing COVID-19, and dose not test statistical hypotheses, so the sample size is set within the limit of satisfying the research purpose. In the Phase I clinical trial, 45 subjects who meet the inclusion and exclusion criteria are registered to secure 15 subjects based on the allocation of each vaccination group. In the Phase Ila clinical trial, it is planned to secure 120 subjects based on randomization.

Randomization is performed 1:1 in 1b and 1c groups of Phase I clinical trial according to the planned random number, and 1:2 in placebo and vaccination groups in Phase Ila clinical trial to determine the difference between placebo and vaccination groups.

6. Analysis Sets

Safety and tolerability analyses will be performed on Safety Set.

✓ **Intention to treat (ITT)**

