Intention to treat (ITT) will include all participants who sign informed consent.

✓ **Modified Intention to treat (mITT)**

Modified intention to treat (mITT) will include all participants who sign informed consent and who have received at least one administration of investigational product. The mITT will be the primary analysis population for baseline and demographic assessments and efficacy outcomes. All subjects will be summarized based on the treatment group to which they were assigned. Since not all subjects will have evaluable immune response data, analysis of immune responses will be performed only for available samples.

✓ **Safety Set (SS)**

Safety Set (SS) will include all mITT participants. The SS will be the primary population for summary and analysis of safety assessments. All subjects will be summarized based on the treatments that actually received.

✓ **Per-Protocol Set (PPS)**

Per-Protocol Set (PPS) will include all mITT participants who complete the trial by receiving all

CONFIDENTIAL

vaccinations and have no significant protocol violations. This set will be used as a sensitivity analysis to summarize the primary and secondary response outcomes. For secondary and exploratory assessments of antibody and T cell immune responses, denominators will include only those participants who are SARS-CoV-2 seronegative at baseline. Unevaluable samples will not be considered as part of the denominator at relevant time points.

Protocol violations that can be excluded from the analysis group include the following and are defined according to the analysis population's definition of 'SOP 0406'.

- Participants who have never been vaccinated with all vaccinations
- Positive for SARS-CoV-2 serum test at Baseline
- Inclusion/Exclusion criteria violation
- Contraindicated drug administration
- Randomization errors
- Vaccination errors
- No blood draw for immunogenicity assessment

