10.5 Vital Signs

The following parameters will be summarized by each timepoint and change from baseline with number of subjects, mean, standard deviation, median, minimum, and maximum by vaccination group.

- Vital Sign parameters: Systolic blood pressure (mmHg), Diastolic blood pressure (mmHg), Heart rate (beats/min), Respiratory rate (breaths/min), Body temperature (°C)

11. Immunogenicity Analysis

Immunogenicity analysis will be performed on mITT, PP with sufficient sample to assay.

The immunogenicity parameters are as follows.

Table 6 In the immunogenicity evaluation category, positivity is classified according to the following criteria.

Immunogenicity			
Endpoints	Parameter	Unit	Criteria for Positive/Negative (or Responder/Non-Responder)
Binding antibody	S-ELISA	Endpoint Titer	Threshold limit to be considered as having a positive response is >50
	ORF3a-ELISA	Endpoint Titer	Threshold limit to be considered as having a positive response is >50
Neutralizing antibody	NEUT	NT ₅₀	Cutoff value on a per-subject basis is defined as: 4x that subject's Day 0 response.
T cell response	ELISPOT	SFU per 10 ⁶ cells	Cutoff value on a per-subject basis is defined as: 2x that subject's Day 0 response. If there is no Day 0 data for that subject, then the cutoff is defined as 2x average Day 0 response for all study participants

CONFIDENTIAL

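### No rule removes baseline-seropositive participants from the primary mITT binding-antibody analysis, and the protocol and SAP definitions then count them in opposite ways

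*SAP*

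**What the plan says.** **Rank of the endpoint.** The protocol synopsis lists under primary endpoints: "Determine of GMT and seroconversion rate of SARS-CoV-2 Spike and ORF3a protein specific binding antibody responses".

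**Population.** SAP 6 states: "The mITT will be the primary analysis population for baseline and demographic assessments and efficacy outcomes". Membership of the mITT needs only consent and one administration. SAP 11 adds: "Immunogenicity analysis will be performed on mITT, PP with sufficient sample to assay".

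**Serostatus rule.** Protocol 11.1 and SAP 6 carry the same sentence. The SAP version is: "For secondary and exploratory assessments of antibody and T cell immune responses, denominators will include only those participants who are SARS-CoV-2 seronegative at baseline". In both documents it stands in the per-protocol paragraph. SAP 6 also lists a positive baseline serum test among the violations that can remove someone from the per-protocol set. Protocol 11.1 plans a separate assessment of baseline seropositives. SAP 6 does not repeat that plan, and SAP 12 leaves the boosting analysis out as already performed.

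**Definition of a positive result.** Protocol 9.2.1 defines seroconversion as an "antibody titer that is below 1:100 at baseline and after vaccination positive at or above the 1:100 dilution". SAP Table 6 gives one criterion for each binding assay: "Threshold limit to be considered as having a positive response is >50". It sets no baseline condition.

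**Where the rate was used.** For entry to Phase IIa, SAP 4.1 required that "the seroconversion rate for the binding antibody responses must be >70" (per cent).

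**The concern.** The plan accepts that baseline seropositives do not belong in an immune-response denominator, but says so only for the lower-ranked endpoints. The endpoint left out is the one whose protocol definition requires a negative baseline. A person at or above 1:100 at baseline contributes to that denominator and can never contribute to the numerator.

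The SAP then classifies binding responders by a different criterion, under which the same person can be a success on arrival. So the plan fixes neither who is counted in the primary rate nor how a seropositive person is scored. A reported rate could be too low or too high depending on which text the programmer follows, and the Phase IIa contrast with placebo is diluted under both. For GMT, pre-existing antibody enters the arm mean whatever the vaccine does.

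**Working it through.** **Inputs from the documents.** Phase I: 15 per arm, 45 in all (protocol 11.6), threshold above 70% (SAP 4.1). Phase IIa: 40 placebo, 80 vaccine (protocol Table S1). Definitions as in protocol 9.2.1 and SAP Table 6.

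**Assumptions, because the documents give no values.** Seropositive fraction s, equal in both arms. True rates among seronegatives of 80% (vaccine) and 2% (placebo). Under Table 6, seropositives stay above 50 at follow-up.

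**The plan's own figure.** The synopsis gives 80% power for a 14-point seroconversion difference with N = 126, that is 84 vaccine and 42 placebo. With a pooled-variance two-proportion test at two-sided 0.05, this reproduces (80.2%) only if the placebo rate is about 0%. At placebo rates of 1%, 2% and 5% the power is 74.2%, 69.0% and 57.4%. The present point does not make that figure wrong. The figure does presuppose almost no positives on placebo, which retained seropositives scored by Table 6 would undo.

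**Step 1: Phase IIa rates.** With true rate p among seronegatives:
- protocol 9.2.1, everyone kept: p(1 − s)
- SAP Table 6, everyone kept: p(1 − s) + s
- difference between arms under either: (0.80 − 0.02)(1 − s)

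| s | 9.2.1: vaccine / placebo | Table 6: vaccine / placebo | Difference (points) |
|---|---|---|---|
| 0 | 80.0% / 2.0% | 80.0% / 2.0% | 78.0 |
| 5% | 76.0% / 1.9% | 81.0% / 6.9% | 74.1 |
| 10% | 72.0% / 1.8% | 82.0% / 11.8% | 70.2 |

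The arm rates move in opposite directions, while the difference shrinks by the same factor. A seronegative denominator restores the first row.

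**Step 2: Phase I, reported rate.** Take one seropositive in an arm of 15, with 10 of the other 14 converting:
- 9.2.1, all kept: 10/15 = 66.7%
- seronegatives only: 10/14 = 71.4%
- Table 6, all kept: 11/15 = 73.3%

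The same data fall on either side of 70% according to the text applied.

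**Step 3: Phase I, chance that one arm exceeds 70%.** Exact binomial, true rate 80%:
- no seropositives, at least 11 of 15: 83.6%
- one kept under 9.2.1, at least 11 of 14: 69.8%
- that person excluded, at least 10 of 14: 87.0%
- that person kept under Table 6, at least 10 of the other 14: 87.0%

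Read as one pooled rate over 45 (at least 32 needed), one person kept under 9.2.1 changes the chance only from 94.8% (32 of 45) to 91.4% (32 of 44).

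**Step 4: GMT.** Suppose one of 40 placebo participants has a titre of 1:3200 and the others are coded 50 (both values assumed). The arm GMT is multiplied by (3200/50)^(1/40) = 1.11, an 11% rise with no vaccine effect.

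**The case against.** **Seropositives should be few or absent.** Exclusion 22 bars a positive antibody or PCR test at screening, exclusion 23 bars prior COVID-19 contact or infection, and protocol 9.2.1 itself assumes a negative baseline. This stands as a limit on size: if there are none, nothing changes. It does not close the gap. Protocol 7.3.7 allows PCR or antibody, so a PCR-only screen can admit a seropositive person. Protocol 2.4 also has a Phase II objective for baseline seropositives, and SAP 6 names them as a ground for per-protocol exclusion.

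**The per-protocol analysis already handles it.** It can, but it is a sensitivity analysis. The main analysis is on the mITT.

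**Randomization and fold-rise protect the comparison.** Randomization balances s between arms in expectation, yet Step 1 assumes exact balance and the difference still shrinks. Fold increase from baseline, which SAP 11.1 plans, does adjust for pre-existing antibody. The arm GMTs and the GMT ratio do not.

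**Keeping every vaccinated participant is defensible in a trial that the SAP calls exploratory and descriptive.** That is fair as a choice of estimand, but the plan does not present it as a choice, and it sits badly with a definition that requires a negative baseline.

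**Stronger readings that the documents do not support.** A reader might infer that the primary rate is biased downwards. That follows from protocol 9.2.1 only; Table 6 reverses it. A reader might also infer that the secondary mITT analyses drop seropositives while the primary keeps them. That needs a sentence in the per-protocol paragraph to govern the mITT, which neither document says. Finally, a reader might infer that entry to Phase IIa is at risk. SAP 4.1 reports Stage 2 in the past tense. The documents also differ on whether the threshold applies to each group (protocol 9.2.1), between groups (protocol 11.5) or as one rate (SAP 4.1), and the seropositive objective is listed for Phase II only.

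**Conclusion.** The concern holds in this form: the serostatus rule omits the primary endpoint, nothing else removes baseline seropositives from the primary mITT binding-antibody analysis, and the two definitions of a positive result score such people in opposite directions. What both definitions share is dilution of the Phase IIa difference by the factor 1 − s: 3.9 points at 5% seropositive and 7.8 points at 10%, with assumed rates of 80% and 2%. The direction of bias in a single arm's rate cannot be stated until the definitions agree.

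The size rests on assumed values of s and of the true rates; s may be zero. The Phase I figures show how a reported rate can depend on the text followed, and cannot bear on a decision already taken. The practical effect is on the Phase IIa and final primary analyses and on how the Phase I rate is described. The point merits correction because the remedy is nearly free, though the numerical effect is probably small.

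**What to change.** 1. In protocol 11.1 and SAP 6, add the primary assessments to the sentence that now names only secondary and exploratory ones.
2. Move it out of the per-protocol paragraph and state that it governs the mITT immunogenicity analyses.
3. Reconcile SAP Table 6 with protocol 9.2.1: add the baseline-negative condition to the seroconversion criterion and use one cutoff in both documents. State how a negative sample is coded, since without that the reader cannot tell whether a titre above 50 and a titre of at least 1:100 select the same people.
4. Keep the separate summary of baseline seropositives from protocol 11.1, restore it in the SAP, and report their number by arm.
5. Show the all-mITT rate and GMT as a sensitivity line, and say which denominator and criterion produced the reported Phase I rate.

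The cost is a wording change, one extra table line, and a denominator smaller by however many participants were seropositive at baseline.

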6.1 Errors in Investigational Product Vaccination

If a subject was not administered with the investigational product that was randomized (planned), the subject will be analyzed according to the following rule:

- If the wrong treatment was used for the entire trial, then he/she will be analyzed according to the actual treatment group for the safety analyses and randomized treatment group for the immunogenicity analyses complying to the intent-to-treat (ITT) principle.
- If the wrong treatment was used for only one of the vaccinations, he/she will be grouped into the highest dose (1.2 mg in Phase I, or treatment arm in Phase IIa) for safety and in the randomized arm for the immunogenicity analyses.

7. General Analysis Considerations

7.1 Statistical Analysis Software

Statistical analyses will be performed using a version 9.4 64bit (SAS Institute, Cary, NC, USA) or higher on the SAS® Enterprise Guide (version 8.2 and later) interface.

CONFIDENTIAL

7.2 General Considerations

Descriptive statistics will be used to summarize the trial results. Continuous variables will be summarized with number of subjects, means, standard deviation (SD), median, minimum, and maximum. Categorical variables will be summarized with frequency and percentage. Unless particularly specified, all tests are based on a two-sided test at a significance level of 5%.

Values that contain decimals such as mean, SD, percentages, etc. will be at the same level as the raw data for medians, minimum and maximum, plus 1 decimal place for means, and plus 2 decimals for SD. All percentages will be presented to 1 decimal place.

Details will be included in listing sorted by phases and by groups.

7.3 Sub Analysis

A sub analysis about safety and immunogenicity is performed for under 65 years and 66-85 years of age.

8. Data Handling Conventions

8.1 Early Termination and Missing Data

In the event that dates and/or times are missing for medications, medications will be assumed to be concomitant. If only partial dates/times are missing and it is clear that medications were discontinued prior to study enrollment, medications will be assumed to be prior. In the event dates or times are missing for AEs, AEs will assume to be treatment emergent. Missing outcomes values, such as missed lab draws or invalid blood sample, missed vital signs, or missed or uninterpretable serum concentrations and PBMCs will be left as missing and not imputed. For the immunology analyses, statistical assessment will be based on available results.

In the event that a participant is enrolled in the trial but declines to be vaccinated, the site will enroll a replacement.

8.2 Handling of Missing Data

If there are missing dates and are used in calculations, they will be imputed as the following:

Table 1 Handling of missing or partial date

Types of Dates	Missing	Imputation	Examples
Prior/ Concomitant medication start date	YYYY-MM-DD	Year of the date of informed consent-01(January)-01	Date of informed consent: 2018-12-05 Collected date: UK-UK-UK Imputed date: 2018-01-01

CONFIDENTIAL

Types of Dates	Missing	Imputation	Examples
	MM-DD	01(January)-01	Collected date: 2018-UK-UK Imputed date: 2018-01-01
	DD	01	Collected date: 2018-12-UK Imputed date: 2018-12-01
Prior/ Concomitant medication end date	YYYY-MM-DD	Final visit date	Final visit date: 2018-12-25 Collected date: UK-UK-UK Imputed date: 2018-12-25
	MM-DD	12-31	Collected date: 2018-UK-UK Imputed date: 2018-12-31
	DD	Last day of the month	Collected date: 2018-12-UK Imputed date: 2018-12-31
AE start date	YYYY-MM-DD	First IP administration date	Date of first IP administration: 2018-12-05 Collected date: UK-UK-UK Imputed date: 2018-12-05
	MM-DD	1. The year of the IP administration date = The year of the AE start date: The month and day of the IP administration date 2. The year of the IP administration date ≠ The year of the AE start date: 01-01	1. Date of IP administration: 2018-12-05 Collected date: 2018-UK-UK Imputed date: 2018-12-05 2. Date of IP administration: 2018-12-05 Collected date: 2019-UK-UK Imputed date: 2019-01-01
	DD	1. The year and the month of the IP administration date = The year and the month of the AE start date: The day of the IP administration date 2. The year and the month of the IP administration date ≠ The year and the month of the AE start date: 01	1. Date of IP administration: 2018-12-05 Collected date: 2018-12-UK Imputed date: 2018-12-05 2. Date of IP administration: 2018-12-05 Collected date: 2019-05-UK Imputed date: 2019-05-01
AE end date	YYYY-MM-DD	1. If the subject is dead: Death date 2. If the subject is not dead and has date of the last observation/date of early termination: Last observation/date of early termination	1. Death date: 2018-12-30 Collected date: UK-UK-UK Imputed date: 2018-12-30 2. Last observation/early termination date: 2018-12-30 Collected date: UK-UK-UK Imputed date: 2018-12-30

